9.3. Data Handling Conventions

For all variables, only the observed data from the patients will be used in the statistical analyses.

9.4. Study Population

The ITT analysis set (see Section 9.2.1) will be used for all open-label efficacy summaries and analyses unless otherwise noted. The safety analyses set will be used for all safety summaries. Summaries will be presented for all patients.

The RRWmITT or RWmITT analysis set (see Section 9.2.5) will be used for all randomized withdrawal efficacy summaries and analyses unless otherwise noted. The RWSAF analysis set will be used for all randomized-withdrawal safety summaries.

9.4.1. Patient Disposition

Data from patients who are enrolled, patients enrolled but not treated (and the reason), patients in the ITT, safety, and other analysis sets, patients who enter the randomized drug withdrawal period, patients who complete the randomized drug withdrawal period, patients who complete the study, and patients who withdraw from the study will be summarized using descriptive statistics. Data from patients who withdraw from the study will also be summarized by reason for withdrawal using descriptive statistics.

9.4.2. Demographic and Baseline Characteristics

Patient demographic and baseline characteristics (day 1), including medical history, prior medications and treatments, and ECG findings, will be summarized using descriptive statistics and will be analyzed by age group. For continuous variables, descriptive statistics (number [n],

mean, standard deviation, median, minimum, and maximum) will be provided. For categorical variables, patient counts and percentages will be provided. Categories for missing data will be presented if necessary.

9.5. Efficacy Analysis

No formal inferential statistics will be applied to the efficacy endpoints in Part A; however, inferential statistics will be applied to the efficacy endpoint in Part B (see Section 9.5.1).

9.5.1. Efficacy Endpoints

The following efficacy endpoints will be assessed in Part A:

- change in the TTS of the YGTSS from day 1 to each visit in which the scale is administered
- change in the Tourette Syndrome-Clinical Global Impression (TS-CGI) score from day 1 to each visit in which the scale is administered
- change in the Tourette Syndrome-Patient Global Impression of Impact (TS-PGII) score from day 1 to each visit in which the scale is administered
- change in the Child and Adolescent Gilles de la Tourette Syndrome – Quality of Life (C&A-GTS-QOL) activities of daily living (ADL) subscale score from day 1 to each visit in which the scale is administered

The following efficacy endpoint will be assessed in Part B:

- change in the TTS of the YGTSS from week 28 to week 30, with the primary analyses and sensitivity testing done as described in Section 9.5.3.1

9.5.2. Exploratory Endpoints

The following exploratory endpoints will be assessed in Part A:

- [REDACTED]
- [REDACTED]
- [REDACTED]
- [REDACTED]
- [REDACTED]
- [REDACTED]
- [REDACTED]

9.5.3. Planned Method of Analysis

The ITT analysis set (see Section 9.2.1) will be used for all efficacy analyses in Part A. Summaries will be presented for all patients.

9.5.3.1. Efficacy Analysis for the Randomized Drug Withdrawal Period

For the randomized drug withdrawal portion of the study, an analysis of covariance model will be used as the primary analysis model with the change from randomized-withdrawal week 28 to week 30 in YGTSS TTS as the dependent variable, and treatment group, randomized-withdrawal week 28 TTS, and age group at baseline as covariates. The least squares mean of the change in TTS from week 28 to week 30 will be compared (the active treatment arm and placebo arm) using a 2-sided test at the $\alpha=0.05$ level of significance.

The primary analysis will be in the RRWmITT population (see Section 9.2.6). In addition, sensitivity testing will be done using the same model in the RWmITT population and in a subpopulation of the RRWmITT who had a $\geq 35\%$ reduction in the TTS from baseline in the parent protocol to week 28.

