3.1.5. Washout Period and Follow-up

All patients will discontinue IMP at the week 54 visit and will return 1 week later (week 55) for evaluation of safety and tic reduction. Patients will have a follow-up telephone contact for safety evaluation 1 week after the end of the washout period (2 weeks after their last dose of IMP) (week 56).

See [Table 1](#) for study procedures and assessments.

See [Figure 1](#) and [Figure 2](#) for study schema.

Part B:

3.1.6. Blinded, Randomized Drug Withdrawal Period and Titration Post-Drug Withdrawal Period (5 Weeks)

At the week 28 visit, the patients will be randomized 2:1 to their current dose of TEV-50717 or placebo in order to check for return of symptoms. Because IMP is dispensed as enough doses for 2 weeks (current dose level and next dose level), the week 28 visit (Day 196) is considered the first day of the randomized withdrawal period, although the patient will begin taking blinded IMP on Day 197. Patients will have a follow-up telephone contact for safety evaluation 1 week after the start of the randomized drug withdrawal period. At week 30, safety and efficacy will be assessed. At the week 30 visit, patients who receive TEV-50717 during the randomized drug withdrawal period will continue at the same dose in a blinded manner from the start of week 31 to the start of week 34. Any patient who was randomized to placebo during this 2-week period will undergo blinded re-titration. Patients will have a follow-up telephone contact for safety evaluation at weeks 31 and 33.

Titration Post-Drug Withdrawal (Weeks 31, 32, and 33)

Any patient who was randomized to placebo between the week 28 and week 30 visits will undergo re-titration to their previously established maintenance dose over the 3 weeks of treatment following the randomized drug withdrawal period (start of week 31 to the start of week 34 [Days 211 through 232]). The titration scheme and maximum dose will be determined based on the previously established maintenance dose according to [Table 3](#). The dose of IMP for each patient who underwent 2 weeks of placebo will be titrated back to the maintenance dose that was used by the patient up to week 28 followed by continued maintenance therapy at that dose.

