9.1. Sample Size and Power Considerations

This study is safety-oriented in nature; therefore, no formal hypothesis testing is planned for Part A. Based on the number of patients in the previous studies, up to approximately 227 patients (approximately 1 patient from the Phase 1b Study SD-809-C-17, up to approximately 99 patients from the Phase 2/3 Study TV50717-CNS-30046, and up to approximately 127 patients from the Phase 3 Study TV50717-CNS-30060) are estimated to enroll.

All patients who complete Study TV50717-CNS-30060 or Study TV50717-CNS-30046 are eligible to participate in Study TV50717-CNS-30047. As the number of patients to be randomized in parent Study TV50717-CNS-30046 has increased, the number of patients anticipated to be randomized into Study TV50717-CNS-30047 has also increased. The rationale for the increased sample size in Study TV50717-CNS-30046 is provided that protocol.

For the randomized drug withdrawal period, 190 patients to be included in the analysis will provide approximately 90% power to detect a difference between TEV-50717-treated and placebo-treated patients assuming a difference in YGTSS TTS of 4.5 with a standard deviation of 9 using a two-sided test for difference at a significance level of 0.05.

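### The Part B primary ANCOVA does not protect the confidence interval if change is more variable on placebo, the smaller arm; a robust or arm-specific variance would do so cheaply

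*Protocol*

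**What the plan says.** Protocol Section 9.5.3.1 states that "an analysis of covariance model will be used as the primary analysis model" for the change in YGTSS TTS from week 28 to week 30, with "treatment group, randomized-withdrawal week 28 TTS, and age group at baseline as covariates". The comparison is two-sided at 0.05. The section adds that "The primary analysis will be in the RRWmITT population" and repeats the same model in two other sets: the wider randomised-withdrawal mITT set and the responders with at least a 35% reduction. It says nothing about the residual variance or the method for the standard error.

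Section 3.1.6 says that at week 28 "the patients will be randomized 2:1 to their current dose of TEV-50717 or placebo". Section 9.1 plans with one spread for both arms: "190 patients to be included in the analysis will provide approximately 90% power to detect a difference", "assuming a difference in YGTSS TTS of 4.5 with a standard deviation of 9". Section 9.5 makes Part B the only part of the study with inferential efficacy statistics.

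**The concern.** An ANCOVA with no further specification estimates one residual variance across both arms. That is harmless if the spreads are equal. With unequal arm sizes and unequal spreads, the standard error of the difference is wrong, and it is too small when the smaller arm is the more variable one.

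The design gives a reason to expect that pattern. Patients kept on drug stay on their dose. Section 3.2 looks for an acute change confined to the placebo group, so any loss of effect is an extra component in that arm only. That loss is unlikely to be the same for everyone: placebo patients come off maintenance doses from 6 to 48 mg (Table 3), and the prior response needed for the primary set starts at 25% (Section 9.2.6). Section 1.3.2.2 reports symptoms re-emerging within a week of stopping in the Phase 1b study, so the loss could show within the two-week window. Unless the loss is negatively related to the rest of the change, its variation widens the placebo spread.

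At stake is whether the interval around the study's one inferential estimate has its stated coverage. Neither sensitivity analysis would reveal a problem, because each changes the population and keeps the model.

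**Working it through.** **Inputs from the protocol.** 190 analysed, 2:1, taken as 127 active and 63 placebo; difference 4.5; SD 9; two-sided 0.05.

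**Input assumed.** R = placebo SD / active SD. The protocol does not give it, so a range is shown.

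**Step 1: the planned power.** SE = 9 × √(1/127 + 1/63) = 1.387. 4.5/1.387 = 3.245, and Φ(3.245 − 1.96) = 0.90. With the t distribution it is 89.8%. The stated figure of approximately 90% reproduces, under one common SD.

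**Step 2: unequal spreads.** Hold the pooled variance at 81. The model-based SE stays at 1.387. The true SE is √(s_P²/63 + s_A²/127). Coverage of the nominal 95% interval is 2Φ(1.96 × 1.387 / true SE) − 1.

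| R (assumed) | SD placebo / active | True SE | Model SE / true SE | Coverage | Power at true SE |
|---|---|---|---|---|---|
| 0.8 | 7.67 / 9.59 | 1.287 | 1.08 | 96.5% | 94% |
| 1.0 | 9.00 / 9.00 | 1.387 | 1.00 | 95.0% | 90% |
| 1.1 | 9.57 / 8.70 | 1.432 | 0.97 | 94.2% | 88% |
| 1.25 | 10.33 / 8.27 | 1.494 | 0.93 | 93.1% | 85% |
| 1.5 | 11.36 / 7.57 | 1.581 | 0.88 | 91.4% | 81% |
| 2.0 | 12.76 / 6.38 | 1.705 | 0.81 | 88.9% | 75% |

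Coverage hardly depends on the number analysed. At R = 1.25 it is also 93.1% with 40/80 and with 30/60 patients.

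**Step 3: what relapse pattern gives which R.** Suppose a fraction q of placebo patients lose L points and the rest lose none, with qL = 4.5. Then Var_P = Var_A + q(1 − q)L², with the n-weighted variance held at 81.

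- 60% lose 7.5 points: q(1 − q)L² = 13.5; SDs 9.5 and 8.7 (R = 1.08); true SE 1.425; coverage 94.4%; power Φ(4.5/1.425 − 1.96) = 88%.
- 30% lose 15 points: q(1 − q)L² = 47.25; Var_A = 81 − (63/190) × 47.25 = 65.3; SDs 10.6 and 8.1 (R = 1.31); true SE 1.517; coverage 92.7%; power 84%.
- 18% lose 25 points, an extreme case: true SE 1.631; coverage 90.4%.

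**Step 4: check on the ANCOVA itself.** In 10,000 simulated trials per setting (63/127, two covariates), the common-variance interval covered 95.2%, 92.9%, 91.5% and 88.3% at R = 1, 1.25, 1.5 and 2. With HC3 standard errors it covered 95.4%, 94.8%, 95.0% and 94.9%. In a separate run with equal spreads, the HC3 standard error averaged 1.012 times the model-based one, about 1% wider.

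**The case against.** The strongest objection is that the protocol states nothing false. It names a model, covariates, alpha and population, but neither imposes a common variance nor fixes a standard-error method. The opening of Section 9 leaves further detail to a statistical analysis plan that is not shown, and variance structure often sits there. This limits the point to an improvement; it is not an error or a contradiction. It does not remove it, because the protocol goes beyond leaving a gap: it fixes a model whose usual form has one variance, plans on one SD, and reuses that model in every listed sensitivity analysis.

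A reader might infer that the placebo spread does grow and that the interval is therefore too narrow. The documents do not support that as fact. They give one SD of 9, no relapse distribution and no arm-specific SD. A reader might also infer that any difference in spread makes the interval too short and the p-value too small. That is wrong: at R = 0.8 the interval over-covers, at 96.5%. Nor is the false-positive rate raised when the drug does nothing to anyone, since both arms then share one variance.

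The size is also modest. The relapse patterns with losses up to 15 points give coverage of about 93% to 94%. The 25-point loss behind 90.4% is hard to reconcile with the 37.6% mean TTS reduction in Section 1.3.2.2, unless patients were losing far more than the average benefit.

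**Conclusion.** The point holds conditionally. Under 2:1 allocation the plain ANCOVA in 9.5.3.1 leaves interval coverage exposed if the placebo change is the more variable one. That is a reasonable expectation from the design, not a documented fact. The shortfall is one to two percentage points in the plausible cases and larger only if the SD ratio reaches 1.5 or more. These figures rest on assumed ratios or relapse patterns with the pooled SD held at the planned 9. Equal spreads give no loss. The two-sided test under no effect in any patient is sound as it stands. Priority: optional, as a cheap improvement to the only inferential analysis.

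**What to change.** In Section 9.5.3.1, keep the model, covariates and populations. Add that the standard error, confidence interval and p-value for the treatment difference will use HC3 robust standard errors, or a residual variance estimated separately by arm with Satterthwaite or Kenward-Roger degrees of freedom. Apply this to the primary analysis and both sensitivity analyses, and settle it before unblinding so that it is not a post hoc choice. If the analysis plan already says so, only a cross-reference is needed.

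The cost is a sentence of text and, with HC3, about 1% in interval width if the spreads are equal. If the placebo spread is larger, the correct standard error is larger too: with 190 patients the stated 90% power becomes about 88% with 60% losing 7.5 points and about 84% with 30% losing 15 points. The robust method does not cause that loss; it reports it. Section 9.1 could say that its 90% assumes equal spreads.

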9.6. Multiple Comparisons and Multiplicity

This does not apply to this study.

9.7. Safety Endpoints and Analysis

Safety analyses will be performed on the safety analysis set (Section 9.2.2) for the open-label study and the RWSAF set for the randomized drug withdrawal portion.

9.7.1. Safety Endpoints

The following safety endpoints will be assessed in Part A (Day 1, Titration, and Maintenance):

- incidence of adverse events
- observed values and changes from day 1 in vital signs
- observed values and changes from day 1 in the CDI-2 (Parent and Self-Report Profiles)
- observed values in the C-SSRS
- observed values in electrocardiogram (ECG) parameters and shifts from parent study baseline (for patients rolling over from Study TV50717-CNS-30046 or Study TV50717-CNS-30060) or from day 1 (for patient[s] rolling over from Study SD-809-C-17) for clinically significant abnormal findings

- observed values and changes from day 1 in clinical laboratory parameters (hematology, serum chemistry, and urinalysis)

The following safety endpoint will be assessed in Part B (Blinded, Randomized Drug Withdrawal Period and Titration Post-Drug Withdrawal Period):

- incidence of adverse events

In addition to routine monitoring of adverse events, clinical laboratory parameters, 12-lead ECGs, and safety scales, an IDMC will monitor safety during the conduct of the study.

9.7.2. Safety Analysis

All adverse events will be coded using the Medical Dictionary for Regulatory Activities. Each patient will be counted only once in each preferred term or system organ class category for the analyses of safety. Summaries will be presented for all adverse events (overall and by severity), adverse events determined by the investigator to be related to IMP (ie, reasonable possibility [see Section 7.1.4] defined as related or with missing relationship) (overall and by severity), serious adverse events, and adverse events causing withdrawal from the study. Patient listings of serious adverse events and adverse events leading to withdrawal will be presented.

Changes in laboratory and vital signs measurement data will be summarized descriptively.

The use of concomitant medications will be summarized by therapeutic class using descriptive statistics. Concomitant medications will include all medications taken while the patient is treated with IMP.

Observed values in ECG parameters will be summarized, and counts and percentages of abnormal findings will be presented. Changes from parent study baseline (for patients rolling over from Study TV50717-CNS-30046 or Study TV50717-CNS-30060) or from day 1 (for patient[s] rolling over from Study SD-809-C-17) in ECG parameters will be summarized descriptively. In addition, the number and percentage of patients with on-treatment QTcF values >450, >480, or >500 msec and change from baseline (Study TV50717-CNS-30046 or Study TV50717-CNS-30060) or day 1 (Study SD-809-C-17) >30 or >60 msec will be presented.

Observed values in the C-SSRS and observed values and changes from baseline in the CDI-2 (Parent and Self-Report Profiles) will be presented for all patients.

If any patient dies during the study, a listing of deaths will be provided, and all relevant information will be discussed in the patient narrative included in the CSR.

9.8. Tolerability Variables and Analysis

Tolerability was not specifically defined.

9.9. Planned Interim Analysis

When approximately 100 patients have completed the 28-week clinic visit, an interim analysis, including data from day 1 and up to week 28 visit only, will be conducted to provide descriptive, long-term safety and efficacy data to be used in regulatory submissions. To maintain data integrity of Study TV50717-CNS-30047, only a limited number of personnel who do not have contact with the sites will have access to this interim data in preparation for the regulatory filing.

As no decisions regarding conduct of the study will be made based on the descriptive interim analysis, no alpha will be spent.

9.10. Reporting Deviations from the Statistical Plan

Deviations from the statistical plan, along with the reasons for the deviations, will be described in protocol amendments, the statistical analysis plan, the CSR, or any combination of these, as appropriate, and in accordance with applicable national, local, and regional requirements and regulations.

10. DIRECT ACCESS TO SOURCE DATA AND DOCUMENTS

The medical experts, study monitors, auditors, IEC/IRB, and inspectors from competent authority (or their agents) will be given direct access to source data and documents (eg, medical charts/records, laboratory test results, printouts, videotapes) for source data verification, provided that patient confidentiality is maintained in accordance with national and local requirements.

The investigator must maintain the original records (ie, source documents) of each patient's data at all times. Examples of source documents are hospital records, office visit records, examining physician's finding or notes, consultant's written opinion or notes, laboratory reports, drug inventory, IMP label records, diary data, protocol-required worksheets, and CRFs that are used as the source (see Section [3.12](#)).

The investigator will maintain a confidential patient identification list that allows the unambiguous identification of each patient. All study-related documents must be kept until notification by the sponsor.

11. QUALITY CONTROL AND QUALITY ASSURANCE

11.1. Protocol Amendments and Protocol Deviations and Violations

11.1.1. Protocol Amendments

No changes from the final approved (signed) protocol will be initiated without the prior written approval or favorable opinion of a written amendment by the IEC/IRB and national and local competent authorities, as applicable, except when necessary to address immediate safety concerns to the patients or when the change involves only nonsubstantial logistics or administration. The principal investigator at each investigational center, the coordinating investigator (if applicable), and the sponsor will sign the protocol amendment.

11.1.2. Protocol Violations

Any deviation from the protocol that affects, to a significant degree, (a) the safety, physical, or mental integrity of the patients of the study and/or (b) the scientific value of the study will be considered a protocol violation. Protocol violations may include non-adherence on the part of the patient, the investigator, or the sponsor to protocol-specific inclusion and exclusion criteria, primary objective variable criteria, or GCP guidelines; noncompliance to the administration of IMP; use of prohibited medications. Protocol violations will be identified and recorded by investigational center personnel in a log or as part of the CRF. All protocol violations will be reported to the responsible IEC/IRB, as required.

When a protocol violation is reported, the sponsor will determine whether to discontinue the patient from the study or permit the patient to continue in the study, with documented approval from the medical expert. The decision will be based on ensuring the safety of the patient and preserving the integrity of the study.

Changes in the inclusion and exclusion criteria of the protocol are **not** prospectively granted by the sponsor. If investigational center personnel learn that a patient who did not meet protocol inclusion and exclusion criteria was entered in a study, they must immediately inform the sponsor of the protocol violation. If such patient has already completed the study or has withdrawn early, no action will be taken but the violation will be recorded.

11.2. Information to Study Personnel

The investigator is responsible for giving information about the study to all personnel members involved in the study or in any element of patient management, both before starting the study and during the course of the study (eg, when new personnel become involved). The investigator must ensure that all study personnel are qualified by education, experience, and training to perform their specific task. These study personnel members must be listed on the investigational center authorization form, which includes a clear description of each personnel member's responsibilities. This list must be updated throughout the study, as necessary.

The study monitor is responsible for explaining the protocol to all study personnel, including the investigator, and for ensuring they comply with the protocol. Additional information will be

made available during the study when new personnel members become involved in the study and as otherwise agreed upon with either the investigator or the study monitor.

